2.5 Timing of final analysis

The primary and secondary outcomes will be analysed at the same time point, following the last visit of the last participant. Analyses corresponding to tertiary objectives will be analysed in the two years after the last visit of the last participant.

2.6 Timing of outcome assessments

The outcomes will be assessed after completion of each treatment regimen (approximately day 28, day 56, day 84). Participants who are unable to attend an on-treatment study visit once their medication has been started (for example due to the COVID-19 pandemic) will be able to restart treatment at the point of stopping treatment if still during the titration phase but otherwise will restart the three weeks of treatment. The washout period can be prolonged as long as is necessary during the COVID-19 outbreak before the next treatment phase is started. If patients experience adverse effects of treatment requiring early cessation of treatment, an early physiological assessment will be offered if possible. All outcomes will be included in the intention to treat analyses, and in per protocol analyses if more than 1 week of treatment has been given, including a dose in the last 24 hours.

2.7 Blinded analysis

A blinded analysis will be undertaken prior to the final data lock to look into the distribution of variables, missing data distributions, outliers and to finalise the per protocol population.

3. Statistical principles

3.1 Statistical significance and multiple testing

All applicable statistical tests will be 2-sided and will be performed using a 5% significance level. 95% confidence intervals presented will be at 95% and two-sided. The 97.5% upper limit will be used in the non-inferiority analysis. No adjustment for multiplicity is planned.

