11.3. The Level of Statistical Significance

At a power level of 0.9, with a 2-sided significance of 5%, a clinically relevant 0.12 unit change in pulsatility index (equivalent to a ~20% difference in risk of recurrent stroke), and conservatively allowing for a standard deviation of differences in PI between repeated measures of 0.2, gives an estimated minimum sample size of 32 patients (paired t-test). Allowing for a 15% drop-out rate, 38 patients would be required. A sample size of 66 achieves 90% power to detect the non-inferiority of sildenafil c.f. cilostazol using a non-inferiority margin of 0.08 (and mean of paired differences 0) at $\alpha=0.025$ (for a 95% CI) with a within-subject variance of 0.02 (equivalent to a SD of differences 0..^{23,24} This equates to 75 patients in total with a 12% drop out rate.

A two-sided 5% significance level will be used for all hypothesis tests.

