1.3 Trial objectives

Primary objective

To assess whether 3 weeks of treatment with sildenafil (a PDE5 inhibitor) reduces cerebral arterial pulsatility on transcranial ultrasound, compared to placebo in patients with chronic vascular injury to the brain (small vessel disease).

Secondary objectives

1. To assess whether 3 weeks of treatment with sildenafil alters cerebral arterial reactivity to carbon dioxide on transcranial ultrasound, compared to placebo (The null hypothesis is that there is no difference in the mean change between the sildenafil and placebo groups)
2. To assess whether 3 weeks of treatment with sildenafil has non-inferior effects on cerebral arterial pulsatility and reactivity to carbon dioxide on transcranial ultrasound, compared to cilostazol (The null hypothesis is that sildenafil is unacceptably inferior to cilostazol i.e. the change in mean flow velocity upon CO₂ challenge with sildenafil differs from that with cilostazol by more than the non-inferiority margin Δ).

3. To assess whether 3 weeks of treatment with sildenafil or cilostazol increases cerebral arterial reactivity to carbon dioxide on MRI, compared to placebo, in normal appearing white matter and within white matter hyperintensities.

Tertiary objectives (exploratory and mechanistic)

1. To assess whether 3 weeks of treatment with sildenafil or cilostazol increases cerebral arterial reactivity to carbon dioxide on MRI, compared to placebo, for all defined cerebral tissue type (all white matter and grey matter) and on a voxel-wise basis.
2. To assess whether there is an increased incidence of adverse events or serious adverse events with sildenafil or cilostazol compared to placebo.
3. To assess whether 3 weeks of treatment with sildenafil or cilostazol affects the following physiological parameters, compared to placebo:
 - a) Systolic and diastolic blood pressure on 1 week of home blood pressure monitoring
 - b) Arterial stiffness (carotid-femoral pulse wave velocity)
 - c) Aortic pulse pressure
 - d) Beat-to-beat and day-to-day variability in systolic blood pressure
 - e) Flow mediated slowing
 - f) Resting state cerebral autoregulation (transfer function analysis derived gain, phase and coherence between beat-to-beat blood pressure and cerebral blood flow velocity during a minimum of 5 minutes of monitoring).

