2.1.3 Tertiary outcome measures

- a) Systolic and diastolic blood pressure will be measured as the mean of the second two readings at each sitting from day 2 to the last day of measurement
- b) Beat-to-beat variability in systolic blood pressure will be measured over 5 minutes as the coefficient of variation (standard deviation / mean) after automated and manual removal of artefacts and after removal of any linear trend in the data.
- c) Flow mediated slowing will be measured as the absolute reduction in speed of flow from the average value during baseline to the minimum valid reading during the first 30 seconds of recovery (assessed blind).
- d) Indices of resting state cerebral autoregulation (transfer function analysis derived gain, phase and coherence) will be determined by transfer function analysis according to the

protocol recommended in the CARNET White Paper, using the open access tfa script developed by [name] and made available via the CARNET collaboration.

- e) A voxel-wise general linear model based analysis of cerebrovascular reactivity on MRI will be performed with the FEAT.
- f) Estimates of CVR will be determined from the peak velocity achieved during each test (hyperventilation, 4% CO₂ and 6% CO₂) minus the baseline value, divided by the peak minus baseline etCO₂ values. Results will be expressed both as absolute and percentage change in mean velocity per mmHg change in etCO₂.

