5.2 Secondary outcomes

The percentage change in mean blood flow velocity per mmHg during inhalation of air, 4% and 6% carbon dioxide versus medical air estimated from the beta-coefficient from a phase-shifted linear regression will be compared between sildenafil and placebo treatment by paired t-test and a 95% confidence interval if normality distribution assumptions hold, or the non-parametric Wilcoxon signed rank test. The analysis will be re-run using the PP population as a sensitivity analysis, and using the percentage change from baseline.

A non-inferiority analysis will be based on the 95% CI for the mean change difference between sildenafil and cilostazol. If the upper 97.5% confidence limit is less than 0.08 units (=inferiority margin, 2/3 of the clinically estimated overall cilostazol effect), non-inferiority will be declared. The data will be transformed if normality assumptions do not hold. The PP population will be used for this analysis, with the ITT population being used in a sensitivity analysis.

Differences in reactivity to CO₂ from baseline in each of three states (sildenafil, cilostazol, placebo) will be compared by mixed-effect general linear models, with post-hoc pairwise comparison, using the ITT population with the PP population being used in a sensitivity analysis. This will apply to both TCD measures of CO₂ reactivity and by ROI on MRI. On MRI, these analyses will also be performed on a voxel-wise basis by use of the FLAME tool (FSL).

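### SAP 3.1 plans no multiplicity adjustment at a 5% level and nothing exempts the exploratory voxel-wise MRI maps, so read as written about 5% of tested voxels would be false positives in each null contrast

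*SAP*

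**What the plan says.** **Error rate.** SAP 3.1: "All applicable statistical tests will be 2-sided and will be performed using a 5% significance level". The same section then says: "No adjustment for multiplicity is planned". Protocol 11.3 is equally general: "A two-sided 5% significance level will be used for all hypothesis tests".

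**Voxel-wise analysis.** In SAP 5.2, reactivity in the three treatment states "will be compared by mixed-effect general linear models, with post-hoc pairwise comparison", for the TCD measures and for MRI regions of interest. The section continues: "On MRI, these analyses will also be performed on a voxel-wise basis by use of the FLAME tool (FSL"). SAP 2.1.3 lists the voxel-wise analysis as a tertiary outcome: "A voxel-wise general linear model based analysis of cerebrovascular reactivity on MRI will be performed with the FEAT". Tertiary objective 1 in SAP 1.3 covers MRI reactivity "for all defined cerebral tissue type (all white matter and grey matter) and on a voxel-wise basis", under the label "Tertiary objectives (exploratory and mechanistic").

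**What is not stated.** SAP 2.1.2 describes the BOLD preprocessing in detail (filtering, motion correction, registration) but gives no inference threshold. Protocol 11.1 mentions only linear models in FSL. SAP 5.4 refers the imaging analysis back to the protocol and the SAP itself. No section gives a voxel-level or cluster-level threshold, a family-wise or false-discovery method, an analysis mask for the maps, a BOLD voxel size or a voxel count.

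**The concern.** Leaving a handful of secondary or exploratory tests unadjusted is a defensible choice if it is declared, as it is here. A voxel-wise map is different in kind, because one contrast contains tens of thousands of tests. At an uncorrected 5% level a map will show flagged voxels whether or not the drug does anything, and spatial smoothness gathers them into clumps that look like regions. The presence of significant voxels then says little about whether there is a drug effect.

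The objective is described as mechanistic, so the natural use of these maps is a statement about where in the brain sildenafil or cilostazol alters reactivity. Such a statement would have 5% control at each voxel but none over the map.

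Timing adds to this. SAP 2.5 has the primary and secondary outcomes analysed together after the last visit, and allows tertiary analyses in the two years after it. A map threshold not fixed in the SAP could therefore be chosen once the main results are known.

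**Working it through.** **Plan's own figure.** There is none to reproduce: the documents give no voxel count and no expected number of false positives. The sample-size calculation in SAP 2.3 concerns MCA-PI and does not bear on this point.

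**Inputs from the documents**
- Per-test level: α = 0.05, two-sided (SAP 3.1, Protocol 11.3).
- Adjustment over voxels: none stated.
- Contrasts: three treatments compared pairwise (SAP 5.2), so 3 × 2 / 2 = 3.

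**Input assumed**
- Number of tested voxels V. Protocol 8.7 gives a voxel size only for the T1 image, not for BOLD. I take a brain volume of 1.0 to 1.4 litres and cubic voxels of 2 to 4 mm.
 - Lower end: 1,000,000 mm³ / 4³ = 15,625, about 16,000.
 - Upper end: 1,400,000 mm³ / 2³ = 175,000.

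**Step 1. Fraction.** With no effect anywhere, each voxel is flagged with probability 0.05. The expected fraction flagged is therefore 5% per contrast. This needs no voxel count and does not depend on correlation between voxels.

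**Step 2. Count.** Expected false positives are 0.05 × V per contrast and 3 × 0.05 × V = 0.15 × V over three contrasts.

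| Voxel side | V (1.0 to 1.4 L) | Per contrast | Three contrasts |
|---|---|---|---|
| 4 mm | 15,625 to 21,875 | 781 to 1,093 | 2,343 to 3,281 |
| 3 mm | 37,037 to 51,851 | 1,851 to 2,592 | 5,555 to 7,777 |
| 2.4 mm | 72,337 to 101,273 | 3,616 to 5,063 | 10,850 to 15,190 |
| 2 mm | 125,000 to 175,000 | 6,250 to 8,750 | 18,750 to 26,250 |

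Reaching 2,000 false positives in one contrast needs V of at least 2,000 / 0.05 = 40,000. Reaching 2,000 over three contrasts needs V of at least 2,000 / 0.15, or 13,334, which is below the whole assumed range.

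**Step 3. Effect of smoothness.** Correlation leaves the mean unchanged but widens the spread. I simulated 150 smooth Gaussian null maps per setting, in an assumed 1.27-litre ellipsoid with an 8 mm smoothing kernel (full width at half maximum).
- 3 mm voxels (V = 47,140): mean fraction 0.0501, middle 95% of counts about 2,040 to 2,720.
- 2 mm voxels (V = 159,024): mean fraction 0.0505, middle 95% of counts about 7,100 to 9,120.

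Smoothness does not rescue the map: the count stays near 5% of V.

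**Step 4. Distance from a controlled threshold.** As an illustration only, Bonferroni control at 5% within one contrast needs a per-voxel p of 0.05 / 50,000 = 1 × 10⁻⁶ at V = 50,000, or 0.05 / 150,000 = 3.3 × 10⁻⁷ at V = 150,000.

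**The case against.** The strongest reply has four parts.

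1. **SAP 3.1 does not prohibit correction.** A reader might infer that it bars any adjustment of the maps. It says only that none is planned, covers tests that are applicable, and does not mention imaging. Correction over voxels is routine in neuroimaging software, and analysts might well apply it. This stands as a point about wording. It does not close the gap: analysts who correct depart from the only multiplicity statement in the plan, and analysts who follow it produce uncorrected maps.

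2. **The absolute counts are not document figures.** A reader might infer that each map would show thousands of false-positive voxels across the whole brain. That rests on a voxel count and a mask that the documents do not give. At 4 mm a single contrast yields only about 780 to 1,090. Whole-brain coverage is an inference from tertiary objective 1, which names all white and grey matter; SAP 5.2 states no coverage. This objection stands. The 5% fraction is unaffected by it.

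3. **The analysis is exploratory.** SAP 1.3 and 2.1.3 class it as tertiary, and the plan does not say that a regional drug claim will be made from the maps. This limits the consequence. It does not remove the problem, since the analysis is pre-specified, also appears in the secondary-outcomes section (5.2), and has a mechanistic purpose.

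4. **Some error control exists.** Each voxel is tested at 5%, so it would be wrong to say there is none. What is missing is control over the map.

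**Conclusion.** The point holds as a confined defect that should be corrected. The plan combines a general no-adjustment statement with a voxel-wise drug comparison, and neither exempts the maps nor says how they are thresholded. Read as written, about 5% of tested voxels would be false positives in each null contrast: about 780 to 8,750 per contrast, or about 2,300 to 26,000 over three contrasts.

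The fraction rests only on the stated 5% level and a valid test at each voxel. The counts rest on the assumed 16,000 to 175,000 voxels and on no treatment difference in any contrast.

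A reader might infer that the trial's main conclusions are at risk. The documents do not support that. The primary MCA-PI comparison and the TCD outcomes do not use these maps, and the secondary MRI outcome is an ROI analysis with two core regions. None of these is affected.

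**What to change.** **SAP 3.1.** Limit the no-adjustment statement to the TCD, ROI and other outcomes that are not voxel-wise.

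**SAP 2.1.3 and 5.2.** State for the voxel-wise maps:
- the mask within which voxels are tested;
- that family-wise error over voxels is controlled at 5% within that mask;
- one named method, fixed before unblinding, for example permutation with threshold-free cluster enhancement, or cluster inference with a stated cluster-forming threshold (if permutation is chosen, say how it relates to the FLAME model already named);
- whether the 5% applies to each contrast or across all three;
- that uncorrected maps are descriptive only.

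Possible wording: *Voxel-wise comparisons of MRI CO2 reactivity are exempt from the no-adjustment statement in section 3.1. Family-wise error over voxels within [mask] is controlled at 5% [per contrast / across the three contrasts] by [method and settings]. Uncorrected maps are shown for description only.*

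**Cost.** A few sentences in the SAP, with no new data and no change to the sample size or to any TCD or ROI analysis. The downside is that fewer voxels will reach the threshold, so a weak or very local drug effect is more likely to be missed on the maps.

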3.2 Adherence and protocol deviations

Compliance with study drugs is assessed by direct questioning at each follow-up visit and by the counting of returned study drug. The number and percentage of participants who adhered to each treatment regimen will be presented in a table by treatment period and group, and overall.

Adherence to treatment is defined as taking at least 80% of prescribed medication during the treatment period (including if treatment ceases early but a physiological assessment is performed), including 3 doses in the last 26 hours before outcome assessment. Protocol deviations (such as errors in applying inclusion/exclusion criteria and missed follow-up visits) will be defined as major or minor prior to unblinding of data, defined in the protocol violation log stored on the CPSD High Compliance Server. The number of patients with major protocol deviations, and the type of deviation will be summarised by treatment sequence group. No formal statistical testing will be undertaken.

3.3 Analysis populations

Intention to treat population The intention to treat (ITT), or full analysis set, population will be all participants randomised, irrespective of eligibility or treatment received. This ITT population will be used for the final analysis corresponding to the primary aim for all participants with available primary outcome data included, and including all patients receiving at least 1 tablet of medication for safety outcomes.

Per protocol population All participants in the ITT population who

- complete each of the treatments for each analysis and

- have no major protocol deviations, prior to unblinding or analysis, leading to exclusion
- are not excluded due to other reasons defined prior to analysis/unblinding
- have had a physiological assessment following at least 1 week of continuous treatment and three trial doses in the last 26 hours.

Safety population

The safety population will consist of all participants who have received at least part of one dose of treatment. This population will be used to summarise the safety (adverse event) data.

4. Descriptive analyses

4.1 Participant throughput

A flow chart template based on the CONSORT guidelines for crossover trials⁴ is provided in Appendix 1, indicating the progress of participants through each stage of the trial.

4.2 Withdrawal from treatment and/or follow-up

Withdrawals from treatment will be reported by treatment group and by arm (treatment sequence allocation group) and specific timepoint. Study withdrawals and loss-to-follow up will also be reported according to treatment sequence allocation and timing of withdrawal (see flow chart template). The proportion of missing outcome data will be given.

4.3 Baseline characteristics

The baseline characteristics of participants will be described, both overall and by treatment sequence allocation group. This will include at least age, gender, incident event (TIA vs stroke), cardiovascular risk factors (history of hypertension, diabetes, smoking), use of concurrent antihypertensive medication and antiplatelet treatment and severity of white matter hyperintensities on eligibility scan (Fazekas scale for MRI, modified Blennow scale for CT). For participants in the MRI substudy, volume of white matter hyperintensities will also be reported. Tests of statistical significance will not be undertaken.

4.4 Unblinding

Any cases of treatment unblinding not pre-specified in the protocol will be listed, together with the reasons for unblinding.

5. Comparative analyses

5.1 Primary outcome

Gosling's MCA-PI will be compared between sildenafil and placebo treatment by paired t-test and a 95% confidence interval if normality distribution assumptions hold, or the non-parametric Wilcoxon signed rank test. If the placebo phase is not available, a comparison between the baseline value and sildenafil period will be accepted. The analysis will be re-run using the PP population as a sensitivity analysis, and using the percentage change at each phase from baseline.

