11. STATISTICS

11.1. Description of Statistical Methods

A statistical analysis plan will be signed off prior to analysis.

Primary outcome :

Change in Gosling's Pulsatility Index from baseline to follow up, utilising the visually-assessed, better quality TCD recording (defined by blinded assessor) will be compared between sildenafil and placebo phases by paired T-test, comparing change in MCA-PI from baseline to after 3 weeks of treatment.

Secondary outcome:

The non-inferiority analysis will be based on the 95% CI for the mean change difference between sildenafil and cilostazol. If the upper 97.5% confidence limit is less than 0.08 units (2/3 of the clinically estimated overall cilostazol effect), non-inferiority will be declared.

Differences in reactivity to CO₂ from baseline in each of three states (sildenafil, cilostazol, placebo) will be compared by mixed-effect general linear models, with post-hoc pairwise comparison.

Tertiary outcomes

Equivalent statistical techniques will be used to determine responses to each of the further physiological measures for sildenafil versus placebo as the primary comparison (paired t-test for continuous outcomes), and mixed-effect linear models across the three groups. MRI imaging outcomes will be compared by analysis tools within the FSL software library, utilising linear models for interaction between drug allocation and BOLD-response to carbon dioxide. Secondly, the relevance of derived physiological indices including home blood pressure, arterial stiffness, cerebral autoregulation, peripheral vascular reactivity and beat-to-beat blood pressure variability will be determined both as predictors of cerebral pulsatility and autoregulation in linear models, and for the interaction between drug class and these indices on cerebral pulsatility and reactivity.

Individuals missing either sildenafil or placebo interventions will be excluded from the analysis corresponding to the primary objective but included in the safety analysis. Participants without cilostazol exposure will be included in the sildenafil-placebo comparison, but not in the - secondary and tertiary analyses.

Safety data will be presented for all patients who are randomised and receive at least one dose of one treatment. Safety data will be summarised descriptively.

Genetic / biochemical predictors of response to treatment will be assessed by mixed linear models for continuous outcomes, and paired t-test for binary measures.

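### SAP 5.2 transforms the non-inferiority data if normality fails, but the 0.08 margin is defined only in raw pulsatility-index units

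*SAP*

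**What the plan says.** **Non-inferiority.** SAP 5.2 defines the quantity: "A non-inferiority analysis will be based on the 95% CI for the mean change difference between sildenafil and cilostazol". Non-inferiority is declared on one condition for the upper 97.5% confidence limit: "less than 0.08 units (=inferiority margin". Straight after that rule comes: "The data will be transformed if normality assumptions do not hold". The SAP does not name the normality criterion, the variable checked, the transformation, or any conversion of the margin. Protocol 11.1 gives the same rule, "If the upper 97.5% confidence limit is less than 0.08 units (2/3 of the clinically estimated overall cilostazol effect), non-inferiority will be declared", and has no transformation clause.

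**Scale of the margin.** SAP 5.2 says only units. SAP 2.3 and Protocol 11.3 settle the scale: 0.08 is used with a within-subject variance of 0.02, beside a primary effect of 0.12 PI units and an SD of paired differences of 0.2. The margin is described as two thirds of the cilostazol effect, which implies an effect of 0.08 ÷ (2/3) = 0.12, the same figure as the clinically relevant PI change.

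**Primary.** SAP 5.1 ties the paired t-test and its 95% interval to normality and otherwise offers an alternative: "or the non-parametric Wilcoxon signed rank test". Protocol 11.1 has no switch: MCA-PI "will be compared between sildenafil and placebo phases by paired T-test, comparing change in MCA-PI from baseline to after 3 weeks of treatment".

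**Blinded review.** SAP 2.7 plans a look at distributions and outliers before data lock. It sets no normality criterion and does not say that the test or transformation is chosen there.

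**The concern.** A non-inferiority margin has meaning only on the scale on which it was justified. Once the data are transformed, 0.08 on the new scale is a different margin, and by how much depends on the transformation and on the level of PI. Applied literally, the rule could pass a drug that is worse by the full raw margin more often than planned, or fail one that is equally good. The trigger is a distributional check with no stated criterion.

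There is also a practical gap. The rule concerns a difference in mean change. Changes from baseline can be negative, so a log cannot be applied to them, and the SAP does not say whether PI or change would be transformed. The branch cannot be carried out without a further decision.

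For the primary, the concern is smaller. The interval is tied to the t-test, so the fallback names no quantity to set beside the 0.12 units used for sizing.

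**Working it through.** **1. Reproduce the plan's figures (SAP 2.3).**
- SD of paired differences: √(2 × 0.02) = 0.20.
- Non-inferiority: n = [0.20 × (1.960 + 1.282) / 0.08]² = 65.7, so 66; 66 / 0.88 = 75. By noncentral t, power at 66 is 89.3%, close to the stated 90%.
- Primary: 32 by noncentral t (power 90.8%); 32 / 0.85 = 37.6, so 38.

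The stated 66 and 75 therefore follow from 0.08 as a raw PI margin with a raw PI SD.

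**2. What 0.08 becomes on another scale.** Let m be the mean PI on cilostazol. The documents give no value, so 0.6 to 1.4 is an assumed range.
- Log scale, 0.08 unchanged: raw margin M = m × (e^0.08 − 1) = 0.0833 × m. It equals 0.08 only at m = 0.96.
- Square-root scale, 0.08 unchanged: M = (√m + 0.08)² − m, which is 0.13 at m = 0.6 and 0.20 at m = 1.4.
- Log margin that would match 0.08 raw: ln[(m + 0.08)/m].

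**3. Effect on the decision (log case).** With n = 66, SE = 0.20/√66 = 0.0246 and t(0.975, 65 df) = 1.997. For a true deficit d, the chance of declaring non-inferiority is Pr[T > 1.997], where T is noncentral t with 65 df and noncentrality (M − d)/SE. Here d = 0.08 gives the false-declaration rate and d = 0 gives the power.

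| Assumed mean PI | Raw margin M | (M − 0.08)/SE | Declared at d = 0.08 | Power at d = 0 | Log margin equal to 0.08 raw |
|---|---|---|---|---|---|
| 0.6 | 0.050 | −1.22 | 0.1% | 52% | 0.125 |
| 0.9 | 0.075 | −0.21 | 1.5% | 85% | 0.085 |
| 1.2 | 0.100 | 0.81 | 12% | 98% | 0.065 |
| 1.4 | 0.117 | 1.49 | 31% | above 99% | 0.056 |
| As planned | 0.080 | 0 | 2.5% | 89% | – |

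A separate calculation on the log scale itself, with log SD = 0.2/m, agrees closely. False declaration was 0.1%, 11.2% and 27.2% at PI 0.6, 1.2 and 1.4 (20,000 simulations each), and power at PI 0.6 was 48%.

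**4. The primary switch.** A Shapiro-Wilk gate at 5% was assumed, since the SAP names none, with 66 pairs.
- Skewed PI values with no treatment effect (exchangeable pairs): the two-stage rule rejected 5.1%, although the gate fired in 88% of runs.
- Normal paired differences, zero mean: 5.0%.
- Heavy-tailed symmetric differences (t with 4 df), zero mean: 4.9%.
- Moderately skewed differences forced to average zero: 7.9%.
- Clearly skewed differences (shifted lognormal, sigma 0.5) forced to average zero: 17.6%, against 5.5% for the t-test alone.

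**The case against.** **A competent analyst would convert the margin or back-transform.** Quite possibly, and the SAP does not say that 0.08 would be carried over unchanged. But it gives no other limit. On the log scale, conversion needs a reference PI that neither document supplies, so the margin would have to be chosen after the data are in hand.

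**The blinded review in SAP 2.7 protects the choice.** It lowers the risk of a choice driven by results. It does not convert the margin, and choosing a transformation is not among its stated tasks.

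**The error need not favour sildenafil.** This is correct. A reader might infer that transforming always loosens the margin. On a log scale it loosens it above a mean PI of 0.96 and tightens it below, at a cost in power. The documents do not show which case applies.

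**A t-test with a signed-rank fallback is common practice.** This stands for the most part. A reader might infer that the primary switch inflates the type I error. The documents do not support that. With no treatment effect, a participant's sildenafil and placebo values are exchangeable, so their difference is symmetric about zero however skewed PI is, and the switch keeps about 5% error. The 17.6% above needs a drug that shifts individuals in a skewed way yet averages exactly zero. A reader might also infer that SAP 5.1 forbids an estimate and interval after a Wilcoxon test. It only omits them, and 0.12 is a sizing input rather than a decision threshold.

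**Conclusion.** The scale mismatch in the non-inferiority rule is real and should be corrected. SAP 5.2 combines a possible transformation with a limit that has meaning only in raw PI units, and Protocol 11.1 does not contain the transformation. Read literally with a log, the chance of passing a true deficit of 0.08 ranges from about 0.1% to 31% over an assumed mean PI of 0.6 to 1.4, and power falls to about 52% at the low end. These figures require that normality is judged to fail, a log is chosen, 0.08 is left unchanged, and the SD of 0.2 and 66 pairs hold. They show sensitivity; they do not predict the result.

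The primary analysis has a minor reporting gap: the fallback branch names no estimate or interval. The Wilcoxon test addresses a different centre from the mean only if treatment makes the paired differences asymmetric.

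**What to change.** **Non-inferiority (SAP 5.2).** Delete the transformation sentence. State that the analysis uses the mean paired difference in MCA-PI, in raw units, with its t-based interval against 0.08 whatever the distribution, and add a bootstrap interval as a sensitivity analysis. Label the margin as PI units, because SAP 1.3 words the non-inferiority null in terms of flow velocity under CO₂. If a transformation is kept, name it, say which variable it applies to, and fix the converted margin and its reference PI before unblinding.

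**Primary (SAP 5.1).** Lead with the mean paired difference and its t-based 95% interval, in line with Protocol 11.1. Report the Wilcoxon test with a Hodges-Lehmann estimate and interval as a sensitivity analysis.

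**Cost.** SAP wording only. The 32/38 and 66/75 stand, and 66 evaluable pairs give 99.8% power for 0.12 by paired t-test. The one drawback is slightly lower efficiency than a rank test if the differences are very heavy-tailed.
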